## 8. Pharmacokinetic/Pharmacodynamic and Exploratory Evaluations

The pharmacokinetics of TAS-205 will not be evaluated in this study. The urine samples for pharmacodynamic evaluation will be collected and treated in accordance with the separately prepared "Procedures for Treatment of Samples for Urine Tetranor-PGDM/-PGEM Concentration Measurement."

#### 8.1 Blood Sampling

Not applicable.

#### 8.2 Urine Sampling

Time points of pooled urine for measurement of individual concentrations and other parameters for pharmacodynamic and exploratory endpoints will be as follows:

- From immediately after waking on the day after initial hospitalization to immediately after waking on the efficacy evaluation day at baseline (the day after start of pooled urine);
- From immediately after waking on Day 4 to immediately after waking on Day 5;
- From immediately after waking on the day after the 2nd hospitalization to immediately after waking on the efficacy evaluation day (Week 12 evaluation); and
- From immediately after waking on the day after the 3rd hospitalization to immediately after waking on the efficacy evaluation day (Week 24 evaluation).

The urine samples will be stored under refrigeration (approximately 4°C) during pooled urine. At each time point of pooled urine described above, parts of the urine will be transferred to urine containers (approximately 4-mL each) and stored frozen (at or below approximately -70°C) at the study site as samples for urine tetranor-PGDM/-PGEM concentration measurement. The frozen samples will then be collected by an externally contracted carrier and analyzed at the Pharmacokinetics Research Laboratories of Taiho Pharmaceutical Co., Ltd.

In addition, at each time point of pooled urine described above, the urine volume (mL) will be calculated from the separately measured urine weight (g) and urine specific gravity (g/mL), and approximately 4-mL each of the urine collected in 2 containers as samples for urine creatinine and creatine concentration measurement at the study site. Urine creatinine and creatine concentrations will be measured at the study site.

For details regarding the collection and treatment of samples for urine tetranor-PGDM/-PGEM concentration measurement, the separately prepared "Procedures for Treatment of Samples for Urine Tetranor-PGDM/-PGEM Concentration Measurement" will be followed.

#### 8.3 Pharmacokinetic Analysis of TAS-205

Not applicable.

#### 8.4 Pharmacodynamic Analysis of TAS-205

The pharmacodynamic analysis is intended to evaluate the inhibitory effect of TAS-205 on PGD2 production through HPGDS inhibition as the mechanism of the pharmacological effect, based on the measured tetranor-PGDM/-PGEM concentrations in the urine samples (pooled urine). Details of the analytical method will be specified in the Statistical Analysis Plan.

# 8.4.1 Calculation of Pharmacodynamic and Exploratory Endpoints

Urinary excretion of tetranor-PGDM, urine tetranor-PGDM/Cre concentration ratio, urinary excretion of tetranor-PGEM, and urine tetranor-PGEM/Cre concentration ratio will be calculated as pharmacodynamic endpoints, and urinary creatinine excretion, urinary creatine excretion, and creatine in urine (%) will be calculated and summarized as exploratory endpoints. Any other calculation of pharmacodynamic and exploratory endpoints will be specified in the Statistical Analysis Plan.

## 8.4.2 Pharmacodynamic and Exploratory Evaluations

The parameters specified below will be evaluated (refer to Section 13.1.3.4, "Analysis of Pharmacodynamic and Exploratory Endpoints") using the pharmacodynamic and exploratory endpoints during pooled urine (refer to Section 8.4.1, "Calculation of Pharmacodynamic and Exploratory Endpoints"). Any evaluation of the detailed analytical method or other parameters will be specified in the Statistical Analysis Plan.

- (1) Effect of TAS-205 on the pharmacodynamic and exploratory endpoints
- (2) Relationship of pharmacodynamic and exploratory endpoints with efficacy endpoints

# 8.4.3 Bioanalytical Method in the Pharmacodynamic Analysis

Urine tetranor-PGDM/-PGEM concentrations will be measured using a validated liquid chromatography/tandem mass spectrometry (LC/MS/MS) assay at the Pharmacokinetics Research Laboratories of Taiho Pharmaceutical Co., Ltd. Urine creatinine and creatine concentrations will be measured using a validated bioanalytical method at the study site.

The urine tetranor-PGDM-/-PGEM and creatinine concentrations will be measured in all subjects in the placebo, low-dose, and high-dose groups.

# 9. Pharmacogenomics

Pharmacogenomic research will not be performed in this study.

# **10. Early Termination or Completion of the Study**

## 10.1 Criteria for Discontinuation of Participation of the Study Site

If the proper conduct of the study is or could be undermined because of significant or continuous non-compliance with GCP or the protocol by the investigator or subinvestigator, the sponsor or the investigator may terminate the study site's participation in the study. In this case, the sponsor or the investigator will report promptly to the Investigational Review Board (IRB) in accordance with the relevant Standard Operating Procedure (SOP) of the study site.

### **10.2** Criteria for Discontinuation of the Study

The sponsor has the right to discontinue the study, regardless of the timing, for administrative reasons. The sponsor will discontinue the whole or part of the study in an appropriate manner if any condition requiring discontinuation is found during the study. In this case, the sponsor will inform the head of the study site of the decision and the reason promptly in writing. The head of the study site will report the decision to the IRB and the investigator promptly in writing. In addition, the investigator or subinvestigator will notify subjects promptly, and change their therapy. The sponsor will notify the regulatory authorities of discontinuation of the study promptly.

## 10.3 Investigations for Individual Subjects at Discontinuation

If a subject is discontinued from the study as specified in Section 4.3, "Discontinuation Criteria for Individual Subjects," the investigator or subinvestigator will take appropriate measures as needed and perform clinical assessments specified for Day 169 (immediately after the end of the administration period) or follow-up test (discontinuation during the follow-up period) (clinical assessments for the safety endpoints) whenever possible. Any adverse event will be followed up whenever possible, as specified in Section 12.1.7, "Follow-up of Adverse Events."

# **11. Efficacy Evaluation**

Among the efficacy endpoints, the motor function and muscle strength of subjects will be evaluated by the sponsor and the master physical therapist in the study in accordance with the evaluation procedure separately prepared. The muscle volume of subjects and other efficacy endpoints will also be evaluated by the sponsor and the muscle volume evaluator in the study in accordance with the evaluation procedure separately prepared.

For efficacy evaluation of serum CK concentration, only the values measured during the hospitalization period will be used in the evaluation.

# **11.1** Training and Prior Certification of Evaluators for Individual Study Sites Before Study Initiation

The evaluators for individual study sites in this study will participate in training on the standardization of motor function and other evaluations in advance. In the training, the reliability of the measurement techniques of evaluators will be assessed, and prior evaluator certification will then be awarded accordingly. The evaluators for individual study sites will preferably be physical therapists; however, if there are limited study staff or other reasons, evaluators with experience in caring for patients with DMD (physicians, occupational therapists, etc.) will be acceptable. The standardized evaluation methods will be specified in separate procedure documents.

#### **11.2 Order of the Efficacy Evaluations**

The various efficacy evaluations will be performed in each subject in a day in the following order:

- Evaluation of muscle volume by BIA, and of lean body mass (evaluations using a body composition monitor; the order of these evaluations will not matter)
- (2) 6MWD test
- (3) Time to rise from the floor test
- (4) Timed Up & Go test
- (5) Timed 10-m walk/run test
- (6) Quantitative muscle strength assessments

The pulmonary function test, muscle volume evaluation by skeletal muscle CT, and serum CK concentration measurement shall be performed by the start of (2) 6MWD test (before start of the motor function test). The evaluations will, in principle, be performed in a consistent order to avoid difference in the order (for all items) for individual subjects in each evaluation period.

# **11.3** Evaluation of Motor Function

The need for repetition of each evaluation (data recollection) will be determined by the evaluator. Any repeated evaluation determined to be necessary for reasons described below will be performed whenever possible, taking into consideration the subject's condition, etc. In this case, the measurement data obtained before the repeated evaluation will not be assessed.

Cases judged to require repeated evaluation: Definite non-compliance with the instruction, marked deviation from the track during the test, reversal of direction of the track, discontinuation during the test for reasons other than fatigue, etc.

### 11.3.1 6MWD Test

The distance the subject can walk as fast as possible in 6 minutes will be evaluated.

The test will be performed using a flat, straight. 25-m track wider than a specified width (a quiet indoor hallway, etc.; the distance will be measured accurately with a tape measure, with marks affixed at both ends and cones placed). The subject will go back and forth along the 25-m distance until completion of the test is announced 6 minutes later (passage time of each 25 m will be recorded). The passage time will be read out to the subject while walking, in a specified timing according to the evaluation procedure. The 6-minute walk distance will be recorded in metric units (distance less than 1 meter will be rounded down). For any subject who falls, information on the time of the fall will be recorded. For details of the preparation, implementation procedures, important points, safety considerations, etc., the evaluation procedure will be followed.

For subjects with 6MWD of less than 75 m in the baseline period, before start of administration in this study, investigational product administration will be started as scheduled (Day 1), and the 6MWD tests after administration (at Weeks 12 and 24) will be performed.

## **11.3.2** Time to Rise from the Floor Test

The time required for the subject to rise from a supine position on the floor as quickly as possible will be evaluated.

The time from start of rising from a supine position to the judgment of standing up (standing posture with arms parallel to the body) will be measured with a stopwatch (unit: second, time measured to 2 decimal places). There is no time restriction for the test. For details of the preparation, implementation procedures, important points, safety considerations, etc., the evaluation procedure will be followed.

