# 4. Patient Inclusion/Exclusion and Subject Discontinuation Criteria

#### 4.1 Inclusion Criteria

Patients who meet all of the criteria below at the enrollment will be included in the study. The rationale is described in Section 14.3.

- (1) A legal guardian (legal representative) of a male pediatric patient with the ability to give consent provides written informed consent to participate in the study (whenever possible, informed voluntary assent should also be obtained personally from the patient after all information has been given in a way that suits the patient's level of understanding).
- (2) Patients with a diagnosis of dystrophinopathy as determined by a dystrophin genetic test or muscle pathology findings, symptoms or signs characteristic to DMD (e.g., proximal muscular weakness, waddling gait, Gowers sign), and progressive walking difficulty at the time of informed consent.
- (3) Patients aged 5 years or more at the time of informed consent
- (4) Patients weighing  $\ge$  7.5 kg and < 60 kg within 14 days before enrollment
- (5) Patients who can rise from the floor or a chair and walk by themselves at the screening test (confirmed by medical interview, actual performance, etc.), with 6MWD of 75 m or more (use of wheelchair in daily activities is permissible)
- (6) Patients who can stay in the hospital for the time period specified in the study
- (7) Patients who can continue with administration of the specified number of tablets
- (8) If the patient is receiving oral steroids for DMD treatment, he had begun the treatment more than 6 months before informed consent, and his symptoms remain stable with no change in the prescription-based dosage regimen of steroids within 3 months

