## **3.4.2** HANDLING OF MISSING VALUES AND ABNORMAL VALUES

For missing values, no imputation will be applied. Data employed at each time point will be used in analysis. For primary and secondary efficacy endpoints, LOCF or MMRM imputation will be applied as needed. The incidence of adverse events, etc. will be analyzed using the analysis set as the denominator.

All measurement data will be used in analysis, except for abnormal values that can be clearly explained, including laboratory values affected by hemolysis at blood collection. Any abnormal value excluded from analysis will be identified, and the rationale for exclusion will be provided.

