- (2) The following analyses will be performed for each value measured in each motor function test (time to rise from the floor test, Timed 10-m walk/run test, Timed Up & Go test), measurement of muscle volume (skeletal muscle CT, BIA), lean body mass, quantitative muscle strength assessments (hip flexion/extension, knee flexion/extension, ankle extension/flexion), serum CK concentration (only the serum CK concentration during the hospitalization period will be used for the efficacy evaluation), and pulmonary function test (VC, FVC, FEV1.0, FEV1.0%): In the analysis of the muscle volume measurement (skeletal muscle CT) in the PPS, the subjects of the reference values will be excluded. See Table 10.1 Method to Derive %MVI (%) for derivation of %MVI (%) of the muscle volume measurement (skeletal muscle CT). In quantitative muscle strength assessments, the maximum values in the measurement without compensation will be used.
  - Summary statistics will be calculated at each time point for each treatment group.
  - Summary statistics for the change from baseline will be calculated, followed by a 2-sample t-test between each treatment group and placebo group at each time point. The data at Week 24 will be analyzed with and without the LOCF imputation.
  - With respect to the above 2 analyses, subgroup analysis will be conducted for the following items.

Subgroup analysis: Presence or absence of the history of steroid use, age category ( $\geq$ 5 years and <7 years, and  $\geq$ 7 years), and baseline 6MWD (<350 m, and  $\geq$ 350 m)

- The treatment effect will be estimated at each time point using the MMRM. The changes from baseline in the values measured at other time points will also be included in this analysis. Covariates will be the assigned group, baseline value, time point, and the interaction term of the assigned group and time point.
- Using the MMRM, the dose relationship will be analyzed at each time point with treatment contrasts of (placebo group, low-dose group, high-dose group) = (-2 1 1), (-1 0 1), and (-1 -1 2). Covariates will be the assigned group, baseline value, time point, and the interaction term of the assigned group and time point.

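### The plan does not say how a boy who cannot complete a timed test is analysed, so losing the task is never scored as the worst outcome

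*Protocol*

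**What the plan says.** Protocol 11.3.2, 11.3.3 and 11.3.4 time each test by stopwatch in seconds to two decimals, and each states "There is no time restriction for the test". All three leave detail to another document: "For details of the preparation, implementation procedures, important points, safety considerations, etc., the evaluation procedure will be followed". Protocol 11.3 lists, as a ground for repeating a test, "discontinuation during the test for reasons other than fatigue, etc". A test stopped through fatigue is therefore not on that list, and no value is assigned to it.

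SAP 3.4.2 gives the default, "For missing values, no imputation will be applied", and then the exception: "For primary and secondary efficacy endpoints, LOCF or MMRM imputation will be applied as needed". For these tests SAP 6.2.1(2) prescribes: "Summary statistics for the change from baseline will be calculated, followed by a 2-sample t-test between each treatment group and placebo group". This applies to every visit, and Week 24 is analysed both with and without LOCF. It also prescribes an MMRM on change from baseline. The LOCF rule in SAP 8.3 carries the most recent non-missing value and does not say whether that may be the baseline.

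Inclusion criterion (5) in Protocol 4.1 admits "Patients who can rise from the floor or a chair and walk by themselves at the screening test". Under Protocol 4.3, needing walking aids at the efficacy evaluations is a reason for withdrawal from administration. Table 1 and Protocol 10.3 limit the assessments after discontinuation to safety endpoints.

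**The concern.** A 6-minute walk distance has a natural low end in metres. A time in seconds has no natural value for a boy who cannot do the task. In this disease, losing the ability to rise or to walk 10 m is the worst result the tests can show, and it is one that a useful drug should delay. A plan with no rule for it treats the result as a missing number, although the number is absent because function was lost.

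The study sets no power target. Protocol 14.1 says that efficacy will be judged on numerical trends, and that endpoints beyond 6MWD and the other motor tests were added so that efficacy can be assessed comprehensively. What is at stake is therefore mainly the arm means and their difference, not a significance test. If one arm loses more boys from a task, the mean change in seconds can hide it.

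**Working it through.** **Plan's own figure.** The only one is the sample size, 3 × 11 = 33, set by feasibility. The documents give no effect size, SD, power or loss rate for these tests, so every rate below is an assumption.

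**Step 1. Follow one boy who is able at baseline and unable at Week 24.**

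- t-test without LOCF: he has no time, so he is omitted. The same holds at Week 12 if he is already unable then, because the SAP applies LOCF only at Week 24.
- t-test with LOCF at Week 24: he stays in, with his Week 12 time or possibly his baseline time (zero change).
- MMRM: a Week 12 time keeps him in, and his Week 24 value is treated as missing at random. If both visits are missing he contributes nothing.
- A boy admitted on rising from a chair who cannot rise from the floor has no baseline floor-rise time, so he has no change score in any of the three.

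**Step 2. How often this could arise.** With loss probability p, the chance of at least one unable boy among n is 1 − (1 − p)^n.

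| p (assumed) | Expected of 11 | At least one of 11 | At least one of 33 |
|---|---|---|---|
| 0.05 | 0.6 | 0.43 | 0.82 |
| 0.10 | 1.1 | 0.69 | 0.97 |
| 0.20 | 2.2 | 0.91 | 1.00 |
| 0.30 | 3.3 | 0.98 | 1.00 |

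**Step 3. Effect on the mean (assumed data).** All 11 active boys slow by 1.0 s. Nine placebo boys slow by 1.0 s, and two (9 s at baseline, 12 s at Week 12) become unable. The active mean change is 1.00 s. The placebo mean change is:

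- without LOCF: 9 × 1.0 / 9 = 1.00 s, no difference between arms
- LOCF from Week 12: (9 × 1.0 + 2 × 3) / 11 = 1.36 s
- LOCF from baseline: (9 × 1.0 + 2 × 0) / 11 = 0.82 s, so placebo looks better than active
- unable set to 30 s: (9 × 1.0 + 2 × 21) / 11 = 4.64 s
- unable set to 60 s: (9 × 1.0 + 2 × 51) / 11 = 10.09 s

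The last two lines show that a ceiling in seconds makes the answer depend on an arbitrary choice. Speed has a natural floor of 0.

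**Step 4. Is LOCF a remedy?** Simulated two-arm trials of 11 v 11 (6,000 runs each), with unable meaning slower than 30 s, give these mean differences (active minus placebo):

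| Unable, placebo v active | Observed cases | LOCF | Unable = 30 s |
|---|---|---|---|
| 4% v 2% | −1.28 s | −1.34 s | −1.66 s |
| 17% v 6% | −2.06 s | −2.06 s | −3.40 s |

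LOCF recovers little or none of the lost difference.

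**Step 5. Separate the scale from the coding.** Assumed: baseline floor-rise speed 0.18/s (SD 0.07), mean loss 0.05 on placebo v 0.02 on active (SD 0.04), unable below 0.03/s, 11 per arm, two-sided 0.05. About 1.0 to 1.2 placebo and 0.4 to 0.5 active boys become unable. Power is about:

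- speed, unable = 0: 0.39
- speed, unable dropped: 0.35
- seconds, unable dropped: 0.18
- seconds, unable set to 33 s (1/0.03): 0.18

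The scale accounts for 0.35 − 0.18 = 0.17, and the coding of unable for 0.39 − 0.35 = 0.04. The mean difference in speed is 0.0299 with zeros and 0.0283 with those boys dropped, an attenuation of (0.0299 − 0.0283) / 0.0299, about 5%. With smaller effects the coding matters less. For losses of 0.03 v 0.01, power is 0.209 with zeros and 0.192 with those boys dropped; for 0.02 v 0.01 (SD 0.03) it is 0.114 and 0.113.

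**The case against.** - **The evaluation procedure may cover it.** It may say how inability is recorded, and it cannot be checked here. This stands as a limit on the claim. It does not settle the analysis: the SAP already carries test-specific derivations, such as the choice of strength values and the %MVI formula, and has none for this.
- **LOCF and MMRM keep these boys in.** This is correct. A reader might infer that a boy who loses the task disappears from every comparison. The SAP does not support that: he is omitted only from the t-tests without LOCF, or from the MMRM if he has no post-baseline time. Elsewhere he is scored too well.
- **The power gain is mostly built in.** This is also correct. A reader might take 0.39 against 0.18 as the cost of discarding unable boys. Step 5 shows that about 0.17 of the 0.21 comes from changing to speed, in a model that draws change as normal in speed, which favours a t-test on speed.
- **The three tests differ.** The missing-baseline issue concerns floor rise only. Inclusion (5) requires independent walking and a 6MWD of at least 75 m, so inability at entry is much less likely for the other two tests.
- **Little depends on it.** These are secondary endpoints, with no power target and no multiplicity control, and the primary 6MWD analysis is a distance. That lowers the severity. It does not remove the point, because a trend in means is distorted whether or not it is tested.
- **Speed departs from the protocol.** Protocol 2.4.2 defines the endpoint as a measured time. This stands, and it is why speed should be added and not substituted.

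**Conclusion.** The gap holds. Seconds have no ceiling, neither document gives an analysis rule for unable, and none of the three planned analyses scores loss of the task as the worst outcome. Boys without a baseline floor-rise time have no change score at all.

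The size is uncertain and depends wholly on assumed loss rates. At 5% loss there is a 0.82 chance of at least one such boy among 33. In the scenario of Step 5, coding unable as 0 is worth about 4 points of power and removes about 5% attenuation. The worked example shows that, in arms this small, two boys can erase or reverse a difference in means. The documents do not support a claim of a known direction or amount of bias in this trial, nor any effect on the primary analysis. Severity is minor to moderate.

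**What to change.** In SAP 6.2.1(2):

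1. Add a t-test and an MMRM of the three tests as speed (1/time for floor rise, 1/time or distance/time for the other two). Code 0 when weakness prevents completion, including at baseline. Leave absences for other reasons missing.
2. Keep the protocol's analysis in seconds alongside it.
3. State that LOCF does not replace an unable result with an earlier time.
4. Report the number unable by arm and visit, and list the boys coded 0.

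The cost is one more derivation, a less familiar unit, and the need to record why a time is absent. That classification should be made before the codes are broken. One limit remains: a boy coded 0 at baseline cannot fall further, so he adds little information on decline, but he is counted and visible.
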